## Specific Aims

This study will employ an innovative and evidence-based digital intervention that includes ten digital assessments (CICADAS app) that will capture data on sensory processing abnormalities and associated cognitive deficits. We will leverage pilot data collected in adolescents with Autism Spectrum Disorder (ASD) and accumulate preliminary evidence for CICADAS app to function as 1) a stand-alone treatment; 2) a primer for PEERS (Program for the Education and Enrichment of Relationship Skills); 3) an enhancer for PEERS. This study will test CICADAS app in adolescents with ASD in a three-arm, active-controlled, randomized crossover trial to document the acceptability and evaluate its potential as a stand-alone treatment, as a primer for PEERS, or as a treatment enhancer of PEERS.

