### Treatment Arms

**Arm A:** Participants assigned to Arm A will engage in CICADAS only for the first 16 weeks of the intervention period. After the completion of the first intervention period and the mid-intervention assessment (V3) visit, these participants will then be assigned to the PEERS only group for the second 16 weeks of the intervention period.

**Arm B:** Participants assigned to Arm B will engage in PEERS + CICADAS for the first 16 weeks of the intervention period. After the completion of the first intervention period and the mid-intervention assessment (V3) visit, these participants will then be assigned to No-Contact (no active intervention) for the second 16 weeks of the intervention period.

**Arm C:** Participants assigned to Arm C will engage in PEERS + Active Control for the first 16 weeks of the intervention period. After the completion of the first intervention period and the mid-intervention assessment (V3) visit, these participants will then be assigned to No-Contact (no active intervention) for the second 16 weeks of the intervention period.

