**Measures of Social Cognitive Functioning:** We designed CICADAS to improve sensory processing abnormalities and social cognition in adolescents with ASD independently and to work in conjunction with PEERS to further enhance response to treatment. Our rationale is that many individuals are unable to process accurately information that underlies social and interpersonal cues. Thus, improving social cognition via targeted training of sensory processing abnormalities should confer an advantage to participants using CICADAS in conjunction with PEERS. The ability of CICADAS to prime the brain for PEERS will be measured through a subject-specific improvement in social cognition. Social cognitive functioning will be assessed a number of ways in order to gauge gains in social skills as well as ecological validity of the intervention. One of these measures will be the PEERS-based Test of Adolescent Social Skills Knowledge (TASSK; Laugeson & Frankel, 2006), a 22-item survey that assesses the teen's knowledge about the specific social skills taught during the intervention. The TASSK is comprised of sentence stems and two possible answers. Total scores range from 0 to 22, with higher scores reflecting greater knowledge of the taught social skills. Additionally, we will include the performance-based Dynamic Affective Recognition Evaluation (DARE) test for socioemotional abilities in the participant as well as parent-report measures (SRS-2, SSIS-RS) in our outcome a battery.

The secondary statistical analysis methodology is a linear mixed model approach. First, we will investigate in the ITT population any differences in baseline demographic, characterization, outcomes variables. Any such factors that show trend level significant differences ( $p < 0.1$ ) will be noted and used as covariates in the linear mixed model analysis. We will examine the data from each outcome measure using a linear mixed model with group and time as fixed factors, and covariates as necessary from the baseline analysis. Missing data will be handled with an iterative maximum likelihood procedure to optimally estimate model parameters. The key value for significance will be the group by time interaction factor for the model. Within-group effect sizes (Cohen's  $d$ ) will be computed using the mean change scores for quantitative outcomes (end-of-treatment minus baseline) and the change score SDs.

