With 48 participants fully evaluated, we will not have enough power to detect a treatment augmentation effect ascribable to CICADAS. However, data from this pilot trial will be used to power a pivotal RCT in Phase II, as they will allow to explore whether:

- a) the concurrent delivery of CICADAS and PEERS for 16 weeks (B1-B2) induces greater improvements sensory processing, cognition, symptom reduction, social skills and behaviors, as well as quality of life, compared to CICADAS only (A1-A2) or PEERS + Active Control (C1-C2) – *preliminary efficacy of CICADAS as a treatment enhancer for PEERS*;
- b) The concurrent delivery of CICADAS and PEERS for 16 weeks (B1-B2) induces greater improvements sensory processing, cognition, symptom reduction, social skills and behaviors, as well as quality of life, compared to the sequential delivery of CICADAS and PEERS (A1-A3) – *preliminary testing of CICADAS as enhancer vs primer*;
- c) improvements sensory processing, cognition, symptom reduction, social skills and behaviors, and quality of life induced by the concurrent delivery of CICADAS and PEERS (B1-B2) are sustained after 16 weeks of no contact (B2-B3) – *durability of augmentation effects*.

To verify these experimental hypotheses, we will conduct the analysis based on the pre-intervention (baseline) and post-intervention data. The criterion for statistical significance is  $p < 0.05$ . Results with  $p < 0.1$  will be described as trends.

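### Hypothesis (a) accepts B versus A as evidence that CICADAS enhances PEERS, but only B versus C holds PEERS constant; the durability claim in (c) also needs Arm C, and (b) compares unequal windows

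*SAP*

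**What the plan says.** The Protocol (Specific Aims) wants to evaluate CICADAS "as a stand-alone treatment, as a primer for PEERS, or as a treatment enhancer of PEERS". Under Treatment Arms, the arms in weeks 0-16 are CICADAS only (A), PEERS + CICADAS (B) and PEERS + Active Control (C). For Arm A the text reads: "Participants assigned to Arm A will engage in CICADAS only for the first 16 weeks of the intervention period". Arms B and C then have 16 weeks without contact. All arms are assessed at weeks 0, 16 and 32 (SAP, Evaluation Time Points).

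The SAP lists three hypotheses at the end of its secondary-outcome text:

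- (a) The B1-B2 change is "compared to CICADAS only (A1-A2) or PEERS + Active Control (C1-C2"). Both comparators sit under one label: "preliminary efficacy of CICADAS as a treatment enhancer for PEERS".
- (b) The B1-B2 change is "compared to the sequential delivery of CICADAS and PEERS (A1-A3"). This is presented as enhancer versus primer.
- (c) It asks whether the Arm B gains "are sustained after 16 weeks of no contact (B2-B3"). The label is "durability of augmentation effects".

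The model is a linear mixed model whose key test is the group-by-time interaction. No pairwise contrasts are named, and the only effect sizes specified are within-group. Significance is p<0.05, and p<0.1 is to be described as a trend. The SAP concedes that power for an augmentation effect is insufficient and says that the data will be used to power Phase II.

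**The concern.** An enhancer claim is a claim about what CICADAS adds to PEERS, so the comparison must keep PEERS the same and vary CICADAS. B versus C does that. B versus A does the reverse: CICADAS is in both arms and PEERS is in one. The Background describes PEERS as an evidence-based treatment supported by several randomised trials, so a PEERS effect is the expected case, at least on social-skills outcomes. As (a) is worded, that effect can be reported as a CICADAS effect.

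The TASSK shows this most directly. It measures "knowledge about the specific social skills taught during the intervention", and by week 16 Arm A has had no PEERS teaching.

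Hypothesis (c) has a related fault. Augmentation is a difference from PEERS without CICADAS, so a change within Arm B cannot show that such a difference lasts.

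At stake is what the pilot can say about enhancement and which effect is taken forward to Phase II.

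**Working it through.** **Inputs.** Arm contents: Protocol, General Study Design and Treatment Arms. Sixteen completers per arm: Protocol, General Study Design. Alpha 0.05: SAP (sidedness is not stated; two-sided assumed). PEERS effect on change scores: not in the documents, so shown over 0.3 to 1.0 SD.

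**The plan's own figure.** The only sample-size arithmetic is 56 recruited for 48 completers at 15% loss. 48 × 1.15 = 55.2, rounded up to 56, reproduces it (48/0.85 = 56.5 would give 57). 48/3 = 16 per arm. No power or effect size is stated for (a) to (c).

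**What each contrast in (a) estimates.** Let T be the change common to all arms, P the PEERS effect, K the CICADAS effect relative to the control games, and I any interaction. Mean change over weeks 0-16:

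- Arm A: T + K
- Arm B: T + P + K + I
- Arm C: T + P

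So B − A = P + I and B − C = K + I. If CICADAS adds nothing (K = I = 0), B − A = P and B − C = 0.

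**Chance of a significant B versus A when CICADAS adds nothing.** Two-sample t test, n = 16 per arm, 30 df, critical value 2.042, noncentrality d × √(16/2) = 2.828d, where d is the PEERS effect in SD of change:

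| PEERS effect d | Noncentrality | B vs A, p<0.05 | B vs A, p<0.1 (trend) | B vs C, p<0.05 |
|---|---|---|---|---|
| 0.3 | 0.849 | 13% | 21% | 5% |
| 0.5 | 1.414 | 28% | 40% | 5% |
| 0.8 | 2.263 | 59% | 71% | 5% |
| 1.0 | 2.828 | 78% | 87% | 5% |

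A simulation (40,000 trials per setting) counting only results in favour of B gave 13%, 27%, 59% and 79% for B versus A, and about 2.5% throughout for B versus C.

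**The overall test.** Approximating the group-by-time interaction by a three-arm ANOVA on change scores, the same simulation with no CICADAS effect gave significance in 13%, 27%, 61% and 81% of trials. It responds to PEERS as B versus A does.

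**Hypothesis (b).** B1-B2 spans 16 weeks and two test sessions; A1-A3 spans 32 weeks and three. With equal treatment effects and a common drift of 0.2, 0.3 or 0.5 SD per 16 weeks, the contrast is biased by that amount and rejects in 8.5%, 13% and 28% of trials. If the drift is improvement, the bias is against B.

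There is also a conflict over what A1-A3 is. The Protocol (General Study Design, Study Procedures/Research, Treatment Arms) gives Arm A PEERS in the second 16 weeks. The SAP (Statistical Plan) says that all three arms have no contact then. On the SAP's account A1-A3 contains no PEERS and is not sequential delivery.

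**Hypothesis (c).** Suppose B equals C at every visit and PEERS gains persist. The augmentation effect is then zero, yet B2-B3 shows no loss. Precision with n = 16: half-width of the 95% CI = 2.131/√16 = 0.53 SD of change. Power to detect a true within-arm loss of 0.5 SD is 46%.

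**The case against.** The strongest reply is that these hypotheses are secondary and exploratory. The primary outcome is feasibility, the sample size was not set by hypothesis testing, and the SAP admits that it cannot detect augmentation. The right contrast, B versus C, is already named in (a). All of this stands, and it limits the severity. It does not cure the label: low power does not change what B versus A estimates, and the SAP still tests at p<0.05.

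The PEERS effect sizes above are assumptions. Hypothesis (a) also covers sensory processing and cognition, and the Background says that PEERS cannot systematically target sensory processing abnormalities. A large PEERS effect on every outcome is therefore not shown. The TASSK is one measure and is in none of the SAP's composites.

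Four stronger readings are tempting, but the documents do not support them:

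- *That the comparator in (b) is invalid.* Arm A is the randomised comparator for sequential delivery as the Protocol describes it, and B2 and A3 are both end-of-treatment points. The defect is the unequal window, which works against B if time and practice bring improvement.
- *That two of the three aims get no randomised answer.* Hypothesis (b) gives the primer aim a randomised comparison with Arm B. What is missing is a comparison of Arm A with PEERS without CICADAS.
- *That a non-significant B2-B3 change will be declared sustained.* The SAP states no such rule. Maintenance within Arm B is a legitimate descriptive question.
- *That Phase II will be sized on B versus A.* The SAP says that pilot data will power Phase II, but not which contrast will be used.

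**Conclusion.** The point holds for (a) and for the label of (c). In weeks 0-16, B versus A estimates PEERS added to CICADAS; if there is an interaction, it is contained in B versus A but cannot be separated there from the PEERS effect. With 16 per arm and no CICADAS effect, B versus A is significant in about 28% of trials at a PEERS effect of 0.5 SD and 59% at 0.8 SD, against 5% for B versus C. This assumes two-sided t tests on change scores with equal SDs and the stated range of PEERS effects. That the contrast answers a different question rests on the arm definitions alone.

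Hypothesis (c) can describe maintenance in Arm B but not durability of augmentation. Hypothesis (b) is usable with its unequal window disclosed, once Arm A's second period is settled.

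This should be fixed, but it does not invalidate the trial: the feasibility outcomes are untouched.

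**What to change.** 1. In (a), specify the B − C difference in change from V1 to V3 as the only enhancer contrast in the mixed model, with its CI. Relabel B − A as the effect of adding PEERS to CICADAS.
2. In (c), report the B − C difference in change from V1 to V4 with a CI as durability of augmentation. Keep B2-B3 as descriptive maintenance within Arm B.
3. In (b), report B1-B2 versus A1-A3 alongside B versus A over V1-V4. State that the first has unequal follow-up and, under the Protocol's schedule, the second has unequal time since treatment.
4. Reconcile the SAP's Statistical Plan with the Protocol's General Study Design, Study Procedures/Research and Treatment Arms on what Arm A receives in the second 16 weeks, because (b) depends on it.
5. Optionally add A versus C as exploratory. At V3 it is a comparison with an active treatment and does not isolate stand-alone efficacy. At V4, under the Protocol's schedule, it has unequal time since treatment.

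The cost is SAP wording; the visits and data are already planned. The downside is that B better than A can no longer be cited as support for enhancement. The remaining contrast is imprecise: the 95% CI half-width for B − C is 2.042 × √(2/16) = 0.72 SD of change, and 80% power needs an effect of about 1.02 SD. That agrees with the SAP's own statement on power.

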## General Study Design

We will employ a three-arm, active-controlled, randomized crossover trial to assess the safety and efficacy of CICADAS app in adolescents with ASD, and to evaluate its potential as a stand-alone treatment, as a primer for PEERS, or as a treatment enhancer of PEERS. We will randomize adolescents with ASD (ages 11-18) to CICADAS only, PEERS + CICADAS app, or PEERS + Active Control app.

Approximately 56 participants will be consented to ensure the successful completion of 48 participants (16 participants per treatment arm). A diagnostic interview will be performed to determine eligibility. Following inclusion and enrollment, participants will complete a set of assessments prior to the intervention to establish their baseline performance. Participants will then be randomized to the CICADAS only group (Arm A), PEERS + CICADAS app group (Arm B), or PEERS + Active Control app group (Arm C) and spend up to 16 weeks engaged in their assigned intervention. After 16 weeks, a full battery of assessments will be administered. For the next 16 weeks, Arm A will continue with PEERS only and Arms B and C will receive no treatment during this period. At the end of the intervention period, a full battery of assessments will be administered a second time to evaluate changes in performance. Finally, participants will be asked to fill out an online exit survey to rate enjoyment, usability, perceived benefits, and ease of fit into schedule.

During the first intervention period, participants assigned to the CICADAS only will complete NB-SCT exercises for 16 weeks. Participants assigned to PEERS + CICADAS will engage with the CICADAS app and complete weekly 1-hour PEERS group sessions for 16 weeks. Participants assigned to receive the PEERS + Active Control will engage in the Active Control app and complete weekly 1-hour PEERS group sessions for 16 weeks. During the second intervention period, participants assigned to receive PEERS only will complete weekly 1-hour PEERS group sessions for 16 weeks. During both intervention periods, these participants may have weekly electronic check-ins with site study personnel (as needed). The CICADAS app and the Active Control app icons, design and user experience will look the same as to not unblind the participants.

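### Durability hypothesis (c) is a no-loss claim, but its only criterion is p < 0.05, with no contrast, margin or interval rule

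*SAP*

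**What the plan says.** The SAP, under Secondary Outcome - Preliminary Efficacy, lists three questions that the data will allow the team to explore. Items (a) and (b) ask whether one regimen improves outcomes more than another. Item (c) asks whether the gains made in Arm B between baseline and week 16 (B1-B2) "are sustained after 16 weeks of no contact (B2-B3"), and labels this "durability of augmentation effects".

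The next paragraph covers all three items together. To verify them, "we will conduct the analysis based on the pre-intervention (baseline) and post-intervention data". It then gives one threshold: "The criterion for statistical significance is" p < 0.05, with p < 0.1 described as a trend.

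The model is described earlier in the same section. It is a linear mixed model with group and time, and "The key value for significance will be the group by time interaction factor for the model". Effect sizes are to be computed from "mean change scores for quantitative outcomes (end-of-treatment minus baseline) and the change score SDs". Nothing in the SAP defines a B2-B3 contrast, a tolerable loss, a retained fraction, an equivalence test or a confidence-interval rule for (c).

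**The concern.** A p-value threshold suits (a) and (b), because each claims a difference and a small p-value supports it. Item (c) claims that a difference is absent. A test of the B2-B3 change has no change as its null hypothesis, so a small p-value can only count against (c), and a large one does not establish it. A smaller or noisier arm makes a large p-value more likely.

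The general model does not fill the gap. A group-by-time interaction over three arms and three visits is not a statement about what Arm B kept between weeks 16 and 32, and the effect size is defined only for end of treatment against baseline.

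The visits are also unclear. The Protocol calls the week-16 visit Mid-Intervention (V3) and the week-32 visit Post-Intervention (V4). In those terms the verification sentence points to B1-B3, while item (c) is labelled B2-B3.

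At stake is what the trial may say about durability, and what is carried into the Phase II trial that these data are meant to inform.

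**Working it through.** **Inputs from the documents**
- Arm B completers: 16. Protocol, General Study Design: "successful completion of 48 participants (16 participants per treatment arm"). Check: 48/3 = 16. The Protocol's Sample Size Justification gives 56 recruited and 15% non-completion: 56 × 0.85 = 47.6, about 48. (Strict inflation is 48/0.85 = 56.5, so 57; the difference is immaterial here.)
- Threshold: p < 0.05, with a trend level of p < 0.1. Sidedness is not stated; two-sided is assumed.

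**Assumptions, because the documents give no figures**
- Gain in baseline SD units: 0.3, 0.5 or 0.8, with equal SD at each visit.
- Retest correlation r: 0.5 or 0.7.
- Complete loss: the true B2-B3 change cancels the whole B1-B2 gain.

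**Chance that a complete loss is non-significant** (within-arm paired t-test, the natural test of B2-B3)
- SD of change = √(2(1 − r)): 1.000 at r = 0.5 and 0.775 at r = 0.7.
- d_z = loss / SD of change; noncentrality = d_z × √16 = 4 × d_z; 15 df; critical value 2.131.
- Example, 0.5 SD at r = 0.5: d_z = 0.500, noncentrality 2.00, power 46.5%, miss 53.5%.
- Example, 0.5 SD at r = 0.7: d_z = 0.645, noncentrality 2.58, power 67.5%, miss 32.5%.

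| Gain, all lost | Miss, r = 0.5 | Miss, r = 0.7 |
|---|---|---|
| 0.3 SD | 79.7% | 69.4% |
| 0.5 SD | 53.5% | 32.5% |
| 0.8 SD | 15.2% | 2.9% |

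**Sensitivity**
- Trend level p < 0.1 (critical value 1.753), 0.5 SD: miss 39.6% and 20.7%.
- Only half the gain lost: 0.5-SD gain, miss 84.5% and 77.3%; 0.8-SD gain, 67.8% and 51.1%.
- Durability examined only after a significant B1-B2 gain (40,000 simulated trials, r = 0.5): miss about 58%, 37% and 11% for 0.3, 0.5 and 0.8 SD.
- Error variance pooled over three arms (about 45 df), r = 0.5: miss 78%, 50% and 12%.

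**What 16 people can show instead**
- 95% half-width for the B2-B3 change = 2.131/√16 = 0.53 change-score SDs, which is 0.53 or 0.41 baseline SDs at r = 0.5 or 0.7.
- A formal retention test (loss below half the gain, one-sided 0.025, true loss zero), in change-score SDs: power 15% for a gain of 0.5 and 32% for 0.8. It would need 128 and 52 people in Arm B for 80% power.
- Rule that the lower 95% limit of the B1-B3 change exceeds zero: a fully lost gain passes in 2.5% of trials. A fully kept gain passes in about 47% (r = 0.5) to 67% (r = 0.7) at 0.5 SD, and in 85% to 97% at 0.8 SD. If half of a 0.8-SD gain is lost, leaving 0.4 SD, it still passes in 32% to 49%. It therefore shows that something remains, not that the gain was kept.

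**The case against.** A reader might infer that the SAP treats a non-significant loss as proof of durability and would often report vanished gains as durable. The documents do not support that. No decision rule for (c) is written, no within-arm test of B2-B3 is named, and the stated test is the group-by-time interaction. If post-intervention is taken in the Protocol's sense, the comparison for (c) may be B1-B3 at p < 0.05. In the direction of benefit, that is the same as a lower 95% limit above zero.

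Nor is a complete loss often missed at every gain size. For a 0.8-SD gain the figure is 15% or 3%, and the trend label lowers the rates further. The documents give neither the gain nor the correlation.

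The setting also matters. The primary outcomes are feasibility, item (c) is one of three exploratory questions, the sample size was set for practical reasons, and the SAP concedes low power for an augmentation effect.

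These points stand, and they make the miss rates conditional and the severity modest. They do not supply a rule for (c). The B1-B3 reading is uncertain, because item (c) is explicitly labelled B2-B3, and even that comparison shows only that some benefit remains. The power concession concerns augmentation, where low power makes a positive finding less likely. If non-significance were read as durability, low power would make a positive finding more likely.

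**Conclusion.** The point holds as a gap in the analysis plan. Item (c) is a no-loss hypothesis whose only stated criterion cannot support it, and the visits named for its verification do not match its label.

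The consequence is conditional. If a non-significant B2-B3 change is taken as sustained, 16 people in Arm B would miss a complete loss in about 80-69% of trials for a 0.3-SD gain, 53-33% for 0.5 SD (40-21% at the trend level) and 15-3% for 0.8 SD. These figures assume a two-sided test, equal SDs across visits and a retest correlation of 0.5 to 0.7; a higher correlation lowers them. The gain sizes are also assumptions. The defect in the criterion does not depend on any of these figures.

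**What to change.** Reword item (c) and the verification paragraph in the SAP:

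1. State that (c) uses weeks 0, 16 and 32.
2. Report the Arm B changes B2-B3 and B1-B3 from the same mixed model, each with a 95% confidence interval.
3. Report the retained fraction, (B1-B3 change)/(B1-B2 change), with its interval. The interval will be wide or uninformative where the week-16 gain is itself close to zero.
4. State that a non-significant B2-B3 change is not evidence of durability.
5. When the lower 95% limit of the B1-B3 change (in the direction of benefit) is above zero, claim only that some benefit remains at week 32, not that the full gain was sustained.

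A formal retention test is not proposed, because Arm B is too small for one.

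The cost is SAP wording; visits, data and model are unchanged. The downside is that fewer outcomes can be called durable: a fully kept 0.5-SD gain would meet the rule in step 5 in only about 47-67% of trials.

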5. *First Intervention Period and Program Use*: Participants who are assigned to receive CICADAS only will be engaged with the NB-SCT exercises for a total of 40 hours during the 16-week period. Participants who are assigned PEERS + CICADAS will be engaged with the NB-SCT exercises for a total of 40 hours and weekly 1-hour PEERS group sessions during the 16-week period. Participants who are assigned to PEERS + Active Control will be engaged with the Active Control app for a total of 40 hours and weekly 1-hour PEERS group sessions during the 16-week period. For PEERS group sessions, Site study personnel will review procedures and guidelines to group sessions and will ask the parent/legal guardian and/or participant to review and sign this form.
6. *Mid-Intervention Assessment (V3)*: Participants will be asked to complete the full battery of assessments performed at baseline.
7. *Second Intervention Period and Program Use*: Participants who are assigned to receive PEERS only will be engaged in weekly 1-hour PEERS group sessions during the 16-week period. The other arms will not receive any treatment during this period.
8. *Post-Intervention Assessment (End of Study Visit; V4)*: After the *Second Intervention and Program Use* period is completed, the participant will be asked to complete the full battery of assessments performed at baseline to assess changes in performance. Duration: ~2 hours remotely or in-person.

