#### Design and Analysis Populations

The Phase I data analysis plan *a priori* defines a primary intent-to-treat (ITT) population, a set of secondary evaluation populations, a set of primary outcome measures, a set of secondary outcome measures, five evaluation time points, a criterion for statistical significance, and a statistical analysis methodology for secondary outcomes.

There are four *a priori* defined analysis populations, including a primary analysis population (i), a secondary analysis population designed to compare effect sizes in populations with no missing data (ii), a population who completed all study visits (iii), and a population that was randomized to access CICADAS.

i. *Intent to Treat (ITT) population*: This is the *a priori* primary analysis population, defined as including all randomized participants who attended at least one PEERS session.

ii. *Intent to Treat (ITT) Fully-Evaluable (FE) population*: This is a secondary analysis population, defined as including all members of the ITT population that complete a post-intervention visit. Note that a participant may complete a specific visit but have missing data for a test in which case the participant is in the overall FE population but does not contribute data to the FE population for that visit, e.g., the number of evaluable cases for a specific test on a specific visit may be smaller than the FE population for that visit because of missing data.

iii. *Intent to Treat (ITT) Completers (C) population*: This is a secondary analysis population, defined as including all members of the ITT-FE population who complete all intervention sessions. Note that the C population is a strict subset of the FE population; a person who completes the treatment but does not complete the post-intervention evaluation visit is not a member of the C population.

iv. *Intent to Treat (ITT) CICADAS-Users (CU) population*. This is a secondary analysis population, defined as all members of the ITT population who have received CICADAS+PEERS, except those who drop/withdraw post-randomization and pre-treatment.

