### Evaluation Time Points

Week 0 –primary and secondary outcome measures are collected on all participants at baseline

Week 16 – primary and secondary outcome measures are collected on all participants

Week 32 – primary and secondary outcome measures are collected on all participants

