### Primary Outcome - Feasibility

Efforts will be made to assess all participants who have completed the minimum required intervention activities: For Arm A (CICADAS only), completing at least 1 hour of NB-SCT; for Arm B (PEERS + CICADAS), completing at least one PEERS group session and 1 hour of NB-SCT; and for Arm C (PEERS + Active Control), completing at least one PEERS group session and 1 hour of games.

As the main goal of this Phase I trial is to evaluate the feasibility, acceptability and usability of the CICADAS app, we will conduct an analysis of the following primary outcome measures in all ITT-CU participants:

1. Digital assessments completion rate. We expect that  $\geq 80\%$  of participants will complete the digital assessment battery at least twice during the CICADAS intervention;
2. NB-SCT program adherence, that is automatically tracked on the back-end data portal (percentage of training sessions completed). Based on our previous studies (CLIMB, MOODIFY, WASABI) and pilot, we expect that  $\geq 70\%$  of participants will complete 20 hours of NB-SCT;
4. Reported side effects (raw score). Based on our previous findings, we expect 0 adverse events due to program use;

5. Overall program completion rate. Based on previous findings from CLIMB and from the pilot in ASD, we hypothesize full program completion in  $\geq 70\%$  study participants.

Secondary Outcome - Preliminary Efficacy

The secondary outcome measures will be collected by trained personnel blind to treatment assignment at baseline, half-way through the intervention, and immediately after the treatment for all randomized participants. Weekly measures will capture the number of initiated or reciprocated social gatherings related to or in addition to PEERS assigned social activities.

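### The SAP writes hypotheses (a) to (c) for weeks 0, 16 and 32, then says they are tested on baseline and post-intervention data, a label the protocol gives to week 32 only

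*SAP*

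**What the plan says.** **Visit labels.** Protocol, Study Procedures/Research, calls the visit after the first 16 weeks "Mid-Intervention Assessment (V3") and the visit after the second 16 weeks "Post-Intervention Assessment (End of Study Visit; V4"). SAP, Evaluation Time Points, lists weeks 0, 16 and 32, the last as "Week 32 – primary and secondary outcome measures are collected on all participants". SAP, Secondary Outcome - Preliminary Efficacy, says the measures are collected "at baseline, half-way through the intervention, and immediately after the treatment for all randomized participants".

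**Second period.** For Arms B and C, Protocol, Treatment Arms, says "these participants will then be assigned to No-Contact (no active intervention) for the second 16 weeks of the intervention period". The same section gives Arm A PEERS in that period. SAP, Statistical Plan, instead gives all three arms no contact.

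**Hypotheses.** The SAP writes (a) as B1-B2 against A1-A2 or C1-C2, (b) as B1-B2 against A1-A3, and (c) as B1-B2 followed by B2-B3. It then states that "we will conduct the analysis based on the pre-intervention (baseline) and post-intervention data".

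**Analysis sets.** SAP, Design and Analysis Populations, describes the Fully-Evaluable (FE) set as "defined as including all members of the ITT population that complete a post-intervention visit". For Completers it adds that "a person who completes the treatment but does not complete the post-intervention evaluation visit is not a member of the C population".

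**Effect size.** Within-group Cohen's d is the end-of-treatment value minus baseline, divided by the SD of the change scores.

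**The concern.** The mid and post labels describe Arm A as the protocol has it: treated in both periods, with V3 half-way and V4 at the end. They do not describe Arms B and C, whose treatment ends at week 16. For them V3 is the end of treatment and V4 is a follow-up visit, so the SAP's statement that the last assessment comes immediately after treatment in all randomized participants is untrue of V4 in two of the three arms.

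The enhancer question in (a) concerns the effect when concurrent treatment ends. At week 32 a B-C difference combines that effect with whatever happens over 16 weeks without contact. Under the protocol's schedule it would also set Arm A just after PEERS against Arms B and C 16 weeks after it. The SAP intends these data to power the Phase II trial, so the visit from which an effect size is taken matters even though no conclusion about efficacy is planned here.

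**Working it through.** **1. Timeline.** V3 = week 16. V4 = 16 + 16 = week 32. Time off treatment at V4 for Arms B and C = 32 - 16 = 16 weeks.

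**2. Is post-intervention week 32 in the SAP too?** The SAP never ties the term to a week. Its text nevertheless fits the protocol's label: the third battery is placed at the end of the intervention, the third listed time point is week 32, and the middle assessment is called half-way.

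**3. Each hypothesis against the data sentence**, taking post-intervention as V4:

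| Hypothesis | SAP indices | Weeks needed | With weeks 0 and 32 only |
|---|---|---|---|
| (a) | B1-B2 vs A1-A2, C1-C2 | 0 and 16, all arms | Not computable as written; only a week 0-32 substitute |
| (b) | B1-B2 vs A1-A3 | Arm B 0 and 16; Arm A 0 and 32 | Arm A side available; Arm B endpoint missing |
| (c) | B1-B2, then B2-B3 | Arm B 0, 16 and 32 | B2 missing; only the net change B1-B3 |

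None of the three can be carried out as indexed.

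**4. Does other SAP text settle it?** The mixed model tests a group-by-time interaction without saying which time levels enter or which contrast answers which hypothesis. End-of-treatment in the Cohen's d definition is week 16 for Arms B and C, but week 32 for Arm A under the protocol's schedule. Design and Analysis Populations announces five evaluation time points; Evaluation Time Points lists three.

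**5. Analysis sets.** The plan's own figures first: 48 / 0.85 = 56.5, against 56 stated; 56 x 0.85 = 47.6, about 48 completers. The documents do not say when losses occur. If the 15% falls evenly over the two periods (assumption):
- retention per period = sqrt(0.85) = 0.922, a loss of 7.8% per period
- seen at V3: 56 x 0.922 = 51.6
- seen at V4: 56 x 0.85 = 47.6
- V3 but no V4: 51.6 - 47.6 = 4.0

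The limits are 0 if all loss precedes V3 and 56 - 47.6 = 8.4 if all follows it. With equal arms, about 4.0 x 2/3 = 2.7 would be in Arms B and C. These are the people the Completers rule can exclude although they may have finished treatment.

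**6. Size of a shift from week 16 to week 32.** Let r be the fraction of the week-16 B-C difference that remains at week 32. The documents give no value for r. The week-32 difference is r times the week-16 difference, and with the SD unchanged a sample size based on it changes by 1/r²:
- r = 1: no change
- r = 0.75: 1/0.5625 = 1.8-fold
- r = 0.5: 1/0.25 = 4-fold
- r = 0.25: 1/0.0625 = 16-fold

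If gains grew after treatment, r would exceed 1 and the error would run the other way.

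**The case against.** The best reply is that the specific governs the general. The visit indices already fix the time points, and the closing sentence can be read loosely as baseline and later data. On that reading nothing is lost. This has force: the indices do suggest that week 16 is meant for (a) and for the Arm B side of (b). It does not remove the conflict, because the closing sentence is the one that says which data verify these hypotheses, and its term has a settled meaning in the protocol.

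The FE definition is also less strict than it may look. It asks for a post-intervention visit, with the indefinite article, and its note speaks of the FE population for a given visit. A participant with V1 and V3 is therefore not clearly excluded from FE. The Completers wording, with the definite article, is harder to read that way.

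The primary population is ITT, analysed by maximum likelihood, so an ITT member with V1 and V3 but no V4 can still contribute. That stands for Arms B and C. ITT membership requires a PEERS session, which Arm A can attend only in the second period, so Arm A's membership is a separate question.

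Finally, end-of-treatment in the Cohen's d definition puts Arms B and C at the same week, 16. This is right, and it limits the damage to the between-group tests and to comparisons with Arm A.

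**Conclusion.** The contradiction is real and should be fixed, at moderate priority. A stated rule, followed literally, gives the wrong visit for (a), no Arm B endpoint for (b) and no week-16 value for (c). Two analysts could follow the SAP and report different visits for the same hypothesis.

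A reader might infer that week-16 data will be ignored, or that the Phase II effect sizes will be diluted. The documents support neither. The indices point to week 16 for (a), the mixed model can use all visits, and the retention fraction r is assumed throughout. The figure of about 4 participants (range 0 to 8.4) rests on an assumed timing of losses and concerns only secondary analysis sets.

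The analyses affected are secondary and exploratory, and the SAP itself says 48 participants give too little power to detect augmentation. The primary feasibility outcomes do not use these contrasts or the FE and Completers sets, and are unaffected.

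**What to change.** 1. Replace the closing sentence after hypothesis (c) with the SAP's own contrasts by week: (a) weeks 0-16 in all arms; (b) Arm B weeks 0-16 against Arm A weeks 0-32; (c) Arm B weeks 0-16 and weeks 16-32. Week 32 must stay where A3 and B3 need it, so substituting V3 for V4 throughout would also be wrong.
2. In the SAP, replace mid-, half-way, post-intervention and end-of-treatment by week 16 or week 32.
3. Define FE and Completers by the visit each contrast needs: V3 for (a); V3 in Arm B and V4 in Arm A for (b); V3 and V4 in Arm B for (c).
4. Report change-score Cohen's d per arm at week 16 and at week 32.
5. Correct the five evaluation time points to three.
6. Reconcile SAP, Statistical Plan (no contact for all three arms) with Protocol, General Study Design and Treatment Arms (Arm A receives PEERS), because the meaning of A3 depends on it.

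Items 1 to 5 cost SAP wording only, since all three visits are already collected from every arm. Item 6 requires the sponsor to settle which text stands. All should be done before outcome data are examined.
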